12.1.2	Compliance with EC Regulations	52
12.1.3	Compliance with Good Clinical Practice	53
12.1.4	Compliance with Electronic Records and Signature Regulations	53
12.2	Changes to the Protocol	53
12.3	Patient Confidentiality and Privacy	53
12.4	Documentation	54
12.4.1	Source Documents	54
12.4.2	Case Report Form Completion	55
12.4.3	Investigator Reports	55
12.4.4	Retention of Documentation	55
12.5	Labeling, Packaging, Storage, and Return of Study Devices	56

12.5.1 Labeling/Packaging.....	56
12.5.2 Storage of Study Devices.....	56
12.5.3 Study Device Accountability.....	56
12.5.4 Return of Study Devices.....	57
12.6 Monitoring by Allergan.....	57
12.7 Publications.....	57
12.8 Coordinating Investigator.....	57
13. References.....	58
14. Attachments.....	59

List of Tables

Table 1-1	Schedule of Visits and Procedures.....	10
Table 6-1	Preoperative Medications.....	29
Table 6-2	Postoperative Medications.....	31

List of Figures

Figure 6-1	XEN Implantation Procedure.....	31
------------	---------------------------------	----

Table 1-1 Schedule of Visits and Procedures

Study Period	Screening ^a	Baseline	Operative day Day 1	Day 2	Day 8	Week 2	Month 1	Month 3	Month 6	Month 8	Month 10	Month 12/ Early exit visit
Visit Window	up to 60 days	Day -5 to Day -7	NA	NA	±2 days	±3 days	±5 days	±10 days	±14 days	±14 days	±14 days	± 14 days
Consent/Authorization	X											
Inclusion/Exclusion Criteria	X	X	X									
Patient Demographics	X											
Medical/Ophthalmic History ^b	X	X										
Patient ocular symptom questionnaire	X							X	X			X
Concomitant Medications, Procedures, Therapies	X	X	X	X	X	X	X	X	X	X	X	X
Adverse Events	X	X	X	X	X	X	X	X	X	X	X	X
Pregnancy Test (Urine) ^c	X	X										X
Study Treatment			X									
Examinations: Recommended to be performed in the following order from top to bottom												
Manifest refraction ^d	OU	OU						SE				OU
Best-corrected visual acuity (Snellen equivalent using LogMar)	OU	OU					SE	SE	SE	SE	SE	OU
Visual Field ^e test	OU											OU ^f
Biomicroscopic slit lamp examination	OU	OU		SE	SE	SE	SE	SE	SE	SE	SE	OU
Intraocular pressure measurement (tonometry) ^g	OU	OU ^h		SE	SE	SE	SE	SE	SE	SE	SE	OU ^h
Pachymetry	OU											OU
Gonioscopy	OU						SE		SE			OU
Ophthalmoscopy ⁱ	OU	OU					SE	SE	SE			OU

NA = not applicable; SE = study eye; OU = both eyes

^a Screening examinations can be completed on more than one visit within the allowable window

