^b Medical history, surgical history, ophthalmic history, and ophthalmic surgical history will be collected

^c Applicable to females of childbearing potential

^d Manifest refraction will be performed during any visit if best-corrected visual acuity (BCVA) reduction of ≥ 2 lines is observed since the last BCVA examination.

^e Visual field test performed up to 6 months prior to operative day (Day 1) is allowed

- ^f If the visual field assessment at this visit shows progression of visual field loss from baseline (defined as a worsening of at least 3 dB in mean deviation score), a second visual field test must be performed within one week to confirm the progression. If the second visual field test is not confirmatory or is equivocal, a third test must be performed within a week to confirm results.
- ^g Measurement of intraocular pressure (IOP) must be performed at Hour 0; IOP must be completed prior to pachymetry, gonioscopy, and ophthalmoscopy.
- ^h Diurnal IOP measurements: Three IOP measurements taken over an eight-hour period on the same day approximately four hours apart, at Hour 0 (\pm 1 hour), Hour 4 = Hour 0 + 4 hours (\pm 30 minutes), and Hour 8 = Hour 0 + 8 hours (\pm 30 minutes)
- ⁱ Non-dilated ophthalmoscopy may be performed if the investigator believes that pupil dilation may put the patient at risk. When dilation is used, ophthalmoscopy should be the last examination.

1. Abbreviations and Terms

Term/Abbreviation	Definition
ACG	angle closure glaucoma
ADE	adverse device effect
AE	adverse event
ALPI	argon laser peripheral iridoplasty
BCVA	best-corrected visual acuity
BID	twice daily
EC	Ethics Committee
eCRF	electronic case report form
EDC	electronic data capture
EU	European Union
FDA	US Food and Drug Administration
GCP	Good Clinical Practice
GON	glaucomatous optic neuropathy
IC	informed consent
ICH	International Conference on Harmonisation
IDFU	investigational directions for use
IOL	intraocular lens
IOP	intraocular pressure
ISO	International Organization for Standardization
ITC	iridotrabecular contact
LPI	laser peripheral iridotomy
OAG	open angle glaucoma
PAC	primary angle closure
PACG	primary angle closure glaucoma
PACS	primary angle closure suspect
PAS	peripheral anterior synechiae
POAG	primary open angle glaucoma
SADE	serious adverse device effect
SITA	Swedish interactive thresholding algorithm
TID	three times daily
USADE	unanticipated serious adverse device effect
QID	four times daily
QD	once daily
WOCF	worst observation carried forward

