5.3 Inclusion Criteria

The following are requirements for enrollment into the study:

Non-ocular Criteria for Inclusion

1. Male or female, ≥ 18 years of age and of legal age of consent
2. Signed written informed consent has been obtained
3. Ability to understand and willingness to follow study instructions and is likely to complete all required visits and procedures

Ocular Criteria for Inclusion

4. Diagnosis of ACG defined as areas of ITC present in ≥ 2 quadrants and glaucomatous damage to optic disc and visual field, in the study eye.

Note: Procedures to widen the iridocorneal angle in the target quadrant (eg, goniosynechialysis, lens extraction [clear lens extraction or cataract surgery/phacoemulsification], and IOL placement) are permitted on the operative day (Day 1) at the investigator's discretion; however, all procedures must be successful and uncomplicated for patients to receive XEN. A maximum of approximately 10 phakic patients (ie, will not undergo lens extraction at time of XEN surgery) is allowed in the study.

5. In the opinion of the investigator, the IOP is uncontrolled in the study eye after having failed previous medical and/or surgical treatment (eg, topical IOP-lowering medications, laser peripheral iridotomy, lens extraction, glaucoma shunt implantation, trabeculectomy)

6. IOP of ≥ 20 mm Hg and ≤ 35 mm Hg by Goldmann applanation tonometry in the study eye at screening and baseline (Hour 0)
7. Study eye has healthy, free, and mobile conjunctiva in the target quadrant
8. Glaucomatous visual field loss with a mean deviation score of at least -1 dB in the study eye that, in the opinion of the investigator, is not functionally significant (eg, split fixation, field defect within the central 10 degrees that is visually significant or likely to cause central visual impairment upon progression are excluded)

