6.1 Procedures to be Performed

Examination visits and visit windows are provided in [Table 1-1](#). The examination requirements for each visit are provided in the following protocol sections and in [Table 1-1](#). It is recommended that the examinations be completed in the order listed, unless otherwise specified.

Visits performed between reporting periods will be documented on an unscheduled visit eCRF. The investigator will report all findings obtained to the sponsor, including IOP measurements, biomicroscopic slit lamp and ophthalmoscopy examination findings, concomitant medications, and AEs.

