6.1.1 Screening Visit

The window for this visit is up to 60 days prior to surgery. After obtaining informed consent ([Section 10.1.2](#)), the following information will be obtained at this visit:

- Evaluation of inclusion/exclusion criteria
- Patient demographics
- Medical history, surgical history, ophthalmic history, and ophthalmic surgical history, including presence of ocular pathology and concomitant ocular medications (both eyes)
- Patient ocular symptom questionnaire

- Concomitant medications (systemic and ophthalmic) and procedures
- AEs
- Urine pregnancy test (for females of childbearing potential)
- Manifest refraction (both eyes)
- BCVA using LogMar chart (both eyes)
- Visual field testing (both eyes): Monocular visual field testing will be measured using the Humphrey 24-2 full threshold program or Swedish Interactive Thresholding Algorithm (SITA) Standard and a reliable, interpretable visual field will be obtained for patients with a preoperative BCVA of better than 20/100. This assessment is not required for patients with BCVA of 20/100 or worse. Visual field results must be reliable and interpretable, or if unreliable or uninterpretable, the visual field test must be repeated. An unreliable visual field is defined as visual field measurements with > 33% fixation losses, false positives, or false negatives. Visual field test performed up to 6 months prior to operative day (Day 1) is allowed.
- Biomicroscopic slit lamp examination (both eyes): includes determination of ophthalmic medical observations/complications, evaluation of the condition of the eyelids, conjunctiva, cornea, anterior chamber, iris/pupil, and lens (through a dilated pupil).
- IOP (Hour 0 = 8:00 am \pm 1 hour) measurement using Goldmann applanation tonometry (both eyes) using the 2-person reading method (See Protocol Procedure Manual); IOP must be completed prior to pachymetry, gonioscopy, and ophthalmoscopy.
- Pachymetry measurement of central corneal thickness (both eyes) using an ultrasonic pachymeter
- Gonioscopy (both eyes): includes assessment of angle abnormalities, such as peripheral anterior synechiae, angle assessment of each quadrant by Shaffer Grade

- Ophthalmoscopy (both eyes): includes dilated fundus evaluation and vertical cup-to-disc ratio. Non-dilated ophthalmoscopy may be performed if the investigator believes that pupil dilation may put the patient at risk.

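### The recommended screening order places a dilated lens examination before screening IOP and gonioscopy, which defeats the purpose of the rule that dilated examination comes last

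*Protocol*

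**What the plan says.** Section 6.1.1 of the protocol lists the screening examinations. The slit-lamp item covers both eyes and includes "iris/pupil, and lens (through a dilated pupil". Tonometry at Hour 0, pachymetry, gonioscopy and ophthalmoscopy follow it.

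The order is recommended in two places. Section 6.1 states "It is recommended that the examinations be completed in the order listed, unless otherwise specified". Table 1-1 introduces its examination rows with "Recommended to be performed in the following order from top to bottom", and those rows run in the same sequence as Section 6.1.1.

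Two rules constrain the order:
- Section 6.1.1 and Table 1-1 footnote g: "IOP must be completed prior to pachymetry, gonioscopy, and ophthalmoscopy".
- Table 1-1 footnote i and Section 7.2: "When dilation is used, ophthalmoscopy should be the last examination".

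An exception to dilation appears in Section 6.1.1, Table 1-1 footnote i and Section 7.2, each time for ophthalmoscopy: "Non-dilated ophthalmoscopy may be performed if the investigator believes that pupil dilation may put the patient at risk".

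Two inclusion criteria in Section 5.3 draw on the later examinations. Criterion 6 requires "IOP of ≥ 20 mm Hg and ≤ 35 mm Hg by Goldmann applanation tonometry in the study eye", at screening and again at baseline Hour 0. Criterion 4 requires "Diagnosis of ACG defined as areas of ITC present in ≥ 2 quadrants", together with glaucomatous disc and field damage.

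**The concern.** The protocol protects IOP by putting it ahead of examinations that could disturb it, and it puts dilated ophthalmoscopy at the end. The screening list nevertheless calls for a dilated pupil at the slit-lamp step, immediately before tonometry. A coordinator working down the list would have the pupil dilated first, then IOP measured, then the angle graded.

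The disease makes this more than a clerical matter. Section 2.1 defines angle closure by contact of the peripheral iris with the trabecular meshwork, which obstructs outflow. Pupil state during tonometry and angle grading is therefore a measurement condition that a protocol would be expected to fix. The protocol itself recognises that dilation can be hazardous in some of these patients, but attaches that recognition to ophthalmoscopy only. An investigator who used the exception at the end of the visit would, on the text, already have dilated the same eye earlier.

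At stake are the conditions under which two entry measurements are taken. Gonioscopy has less protection than IOP, because Table 1-1 schedules it only once before surgery.

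**Working it through.** No arithmetic applies. The check sets the passages side by side.

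**1. The listed order.** Table 1-1 and Section 6.1.1 give the same eight examinations: (1) manifest refraction, (2) BCVA, (3) visual field, (4) slit lamp, (5) IOP, (6) pachymetry, (7) gonioscopy, (8) ophthalmoscopy. The dilated lens view belongs to step 4. Four examinations follow it, and two of those, steps 5 and 7, bear on criteria 6 and 4.

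**2. Does another rule override step 4?** Section 6.1 lets the order yield where something else is specified, so each rule has to be tested.
- IOP-first rule: it names steps 6, 7 and 8. It does not name the slit lamp or dilation, so step 4 may precede step 5.
- Dilation-last sentence: it names step 8, which is already last. It does not reach a dilated step 4.
- At-risk exception: it covers step 8 only.

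None of the three moves step 4.

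**3. Where else is a dilated slit-lamp examination stated?** Only in Section 6.1.1. The slit-lamp items for baseline (Section 6.1.2) and follow-up (Section 6.1.4) do not mention dilation. The general description in Section 7.2 includes the lens, again without dilation.

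**4. Which measurements have a second scheduled reading before surgery?**
- IOP: yes. Criterion 6 applies at screening and at the baseline visit.
- Gonioscopy: no. Table 1-1 schedules it at screening and then at Months 1, 6 and 12.

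The documents do not say outright that iridotrabecular contact is judged by gonioscopy. It is, however, the only listed examination that grades the angle quadrant by quadrant.

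**5. Where is the screening reading used in the analysis?** The primary endpoint uses baseline Hour 0 IOP (Protocol 8.2.1), and SAP 10.1.1 takes it from the Hour 0 IOP eCRF page for the Baseline visit. SAP 16.1 selects the assessment closest to Day 1 within the baseline window, which again points to the baseline visit 5 to 7 days before surgery. Screening IOP is only tabulated, as a baseline characteristic (SAP 8.2). Gonioscopy enters no primary or secondary effectiveness variable, and SAP 11.3 summarises it by visit.

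**The case against.** The case on the other side is substantial.

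- **The order is not binding.** Both statements of it are recommendations, and Table 1-1 footnote a allows screening examinations to be spread over more than one visit. A site could leave the lens view until the dilated fundus examination without a deviation. This stands: dilation before IOP is not forced. It remains what the written sequence tells a site to do.
- **The wording appears once.** A single parenthesis at screening is thin evidence that the sponsor wants dilation before tonometry, particularly as a separate dilated fundus evaluation ends the same list. This also stands as a reading of intent, and it is a reason to correct the text.
- **The Protocol Procedure Manual is not available here.** It may settle the sequence. That limits confidence about what sites did or would do, but it does not repair the protocol text.
- **Unscheduled gonioscopy is allowed** (SAP 16.2), so a second angle reading is possible. None is scheduled before surgery.

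A reader might also infer three stronger things that the documents do not support. One is that the list contradicts the dilation-last sentence; it does not, because that sentence governs ophthalmoscopy and ophthalmoscopy is listed last. Another is that later angle grades will be analysed as change from a dilated screening value. SAP 11.3 plans by-visit summaries of gonioscopy and states no change from screening, whereas it does plan change summaries for pachymetry and visual field. Angle-widening procedures allowed on Day 1 could in any case change the angle between screening and follow-up. The third is that the dilated slit-lamp wording carries over to the baseline visit and so reaches the primary endpoint; Section 6.1.2 does not say so.

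**Conclusion.** The point holds as a sequencing defect in the screening instructions. The recommended order puts a dilated lens examination ahead of screening IOP and of the only scheduled preoperative angle grading, and no rule in the protocol moves it. The purpose of keeping dilated examination to the end is defeated, though the sentence expressing it is not literally broken.

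Its reach is limited. It concerns patients at sites that follow the list within a single visit. The IOP criterion has a second check at baseline, and the primary endpoint does not rest on the screening reading. What is left largely unprotected is the angle grading that bears on criterion 4.

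It would go too far to say that eligibility measurements are biased. The documents give neither a direction nor a size for the effect of dilation on IOP or Shaffer grade, so no number of wrongly included or excluded patients can be derived.

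The conclusion assumes that sites tend to follow a recommended order, that the Procedure Manual does not already set a different one, and that gonioscopy is how iridotrabecular contact is established.

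**What to change.** Reword Section 6.1.1 and Table 1-1 so that any lens assessment through a dilated pupil comes after IOP and gonioscopy, alongside the dilated ophthalmoscopy. The undilated part of the slit-lamp examination can stay where it is. It would help if the ordering rule referred to dilation itself as well as to ophthalmoscopy, so that the rule and the list agree wherever a dilated step appears.

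Separately, the sponsor should reconcile the passages on the at-risk dilation exception. They should say whether it applies to the lens examination as well as to ophthalmoscopy. Its clinical content is for the sponsor to decide.

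The cost is a wording change in the protocol, carried into the Procedure Manual if that repeats the sequence. No examination or visit is added, and the analysis is unchanged.

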6.1.2 Baseline Visit

Baseline visit must be performed 5 to 7 days before the surgery. The following tests must be performed on the baseline visit prior to the initiation of preoperative corticosteroid treatment:

- Evaluation of inclusion/exclusion criteria
- Medical history, surgical history, ophthalmic history, and ophthalmic surgical history, including presence of ocular pathology and concomitant ocular medications (both eyes)
- Concomitant medications (systemic and ophthalmic [both eyes]) and procedures
- AEs
- Urine pregnancy test (for females of childbearing potential)
- Manifest refraction (both eyes)
- BCVA using LogMar chart (both eyes)
- Biomicroscopic slit lamp examination (both eyes)
- Diurnal IOP measurement (both eyes): Three IOP measurements taken over an 8-hour period on the same day approximately 4 hours apart, at Hour 0 (± 1 hour), Hour 4 = Hour 0 + 4 hours (± 30 minutes), and Hour 8 = Hour 0 + 8 hours (± 30 minutes). As scheduling permits, the patient must have approximately the same Hour 0 time of day throughout the study. IOP must be completed prior to ophthalmoscopy.
- Ophthalmoscopy (both eyes)

6.1.2.1 Preoperative Medications

At the baseline visit, patients will be prescribed and instructed to self-administer the following preoperative medications in [Table 6–1](#) (See Protocol Procedure Manual). If

medications in Table 6–1 are not allowed as per local laws and/or regulations, investigator’s standard practice may be substituted based on prior discussions with the sponsor. All preoperative medications will be recorded in the eCRF.

Table 6–1 Preoperative Medications

Medication	Dose	Duration
Topical broad spectrum ophthalmic antibiotic, recommended without preservative (See Protocol Procedure Manual)	QID	One day prior to surgery
Topical corticosteroid: difluprednate 0.05% or prednisolone acetate 1% or equivalent (See Protocol Procedure Manual)	QID	5 to 7 days prior to surgery, per investigator’s discretion

QID = 4 times daily

Patients must be instructed to discontinue all topical and systemic IOP-lowering medications on the day of surgery.

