4.4 Permissible and Prohibited Medications/Treatments

4.4.1 Permissible Medications/Treatments

Use of concomitant medications other than the prohibited medications (Section 4.4.2) is allowed. The use of any concomitant medication or procedure, prescription or over-the-counter, is to be recorded on the patient's electronic case report form (eCRF) at each visit along with the reason the medication is taken. Prior medications will be recorded as part of the medical history on the participant's eCRF during the first study visit.

Therapy considered necessary for the patient's welfare may be given at the discretion of the investigator. If concurrent medications may have an effect on study outcomes, these medications must be administered in dosages that remain constant throughout the entire duration of the study. If the permissibility of a specific medication/treatment is in question, please contact the sponsor.

Treatment of the fellow (non-study) eye is not restricted, and fellow eyes will receive appropriate medical and/or surgical treatment, including IOP-lowering medications, per the investigator's discretion.

Use of ocular decongestants or antihistamines is allowed if not taken within 2 days prior to a scheduled visit. Ocular decongestants or antihistamines may be restarted 3 days after implantation per the investigator's discretion.

Systemic beta-blocker containing medications are permitted, provided that the dose/dosing regimen has remained stable for at least 2 months prior to screening and is not anticipated to change throughout the duration of the study.

The use of systemic nonsteroidal antiinflammatory drugs is also permitted.

Procedures to widen the iridocorneal angle in the target quadrant (eg, goniosynechialysis, lens extraction [clear lens extraction or cataract surgery/phacoemulsification], and intraocular lens [IOL] placement) are permitted on the operative day (Day 1) at the investigator's discretion; however, all procedures must be successful and uncomplicated for patients to receive XEN. If there are complications that would be significant enough to impact the study results, the patient will be exited from the study. Such complications include, but are not limited to, severe corneal burn, vitreous removal/vitreotomy required, severe anterior chamber injuries, or complications requiring the placement of an anterior chamber lens.

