4.4.1.1 IOP-lowering Medications

Systemic and topical (study eye only) IOP-lowering medications, will be suspended on the day of surgery (operative day [Day 1]); no washout period is required. They may be introduced postoperatively to manage elevated IOP. At least one of the following criteria must be met to introduce IOP-lowering medications postoperatively:

- Investigator determines IOP is not at target for the patient
- Progression of optic nerve cupping (vertical cup-to-disc ratio)
- Progression of visual field loss (confirmed with a second visual field test within one week).

It is recommended that the medications are prescribed in a step-wise fashion by introducing one drug class at a time. Prior to changing the first postoperative medication or adding subsequent medication(s), the medication must be maintained at a dosage and frequency recommended by the manufacturer's labeling for a reasonable trial period (eg, 1 week). Investigators will consider any contraindications the patient may have previously experienced (eg, allergic reaction or lack of efficacy) and/or the patient's current clinical situation. All changes to the IOP-lowering medication regimen, topical and systemic, will be recorded on the appropriate eCRF.

The investigator may consider discontinuing or lowering the dose or frequency of IOP-lowering medications whenever it is in the interest of patient safety, eg, cases of hypotony (IOP falls below 6 mm Hg).

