4.4.2 Prohibited Medications/Treatments

The decision to administer a prohibited medication/treatment is done with the safety of the study patient as the primary consideration. Therapy considered necessary for the patient's welfare may be given at the discretion of the investigator. When possible, the sponsor is to be notified before the prohibited medication/treatment is administered.

Topical and systemic IOP-lowering medications must be suspended on the day of surgery (operative day [Day 1]); no washout period is required. If required, IOP-lowering medications may be introduced postoperatively to manage any elevated IOP (Section 4.4.1.1).

Use of contact lens in the study eye is prohibited during the study.

The following medications (or classes of medications) and treatment procedures are not permitted as concurrent therapy:

- Surgical procedures not related to XEN administration and postoperative management, including other incisional glaucoma treatments, such as trabeculectomy or glaucoma shunt implantation in the study eye, during the study period

- Laser glaucoma treatments, such as laser peripheral iridotomy and laser trabeculoplasty, in the study eye during the study period
- Subconjunctival, sub-Tenon's, intravitreal, or other ophthalmic injections of any medications in the study eye during the study period, with the exception of any medications required for bleb management (Section 6.1.3.2.2)
- Use of any nonstudy topical ophthalmic medications in the study eye, including use of IOP-lowering medications without meeting the criteria specified in Section 4.4.1.1, during the study period, with the exception of ocular decongestants or antihistamines (Section 4.4.1)
- Use of any ophthalmic (including topical, intravitreal, sub-Tenon's, subconjunctival) corticosteroids in either eye from 2 months prior to the baseline visit through study exit, except for use of preoperative, operative, and postoperative topical ocular corticosteroids related to surgery
- Initiation of or alterations in oral, intramuscular, or intravenous corticosteroids from 2 months prior to the baseline visit through the study exit
- Use of LATISSE® (bimatoprost for hypotrichosis) during the study period in the study eye

5. Study Population

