6.1.3 Operative Visit (Day 1)

Patients must be scheduled for surgery within 60 days of screening. The following procedures must be performed prior to the implantation of study treatment:

- Evaluation of inclusion/exclusion criteria
- Medical history, surgical history, ophthalmic history, and ophthalmic surgical history, including presence of ocular pathology and concomitant ocular medications (both eyes)
- Concomitant medications (systemic and ophthalmic [both eyes]) and procedures
- AEs
- Urine pregnancy test (for females of childbearing potential)

The implantation procedure must be performed in an approved surgical suite or operating room using standard aseptic technique and standard ophthalmic surgical techniques to prepare the patient and the operative study eye. Preoperative and intraoperative surgical medications will be administered as customary for the investigator.

[figure not shown]
It is recommended that the target quadrant be the superior nasal quadrant, unless conjunctival scarring will inhibit bleb formation. If implantation is not possible in this quadrant, the order of preference for Gel Implant location is superior temporal, inferior nasal, and lastly inferior temporal.

A detailed description of the XEN surgical procedure is provided in the Protocol Procedure Manual. The general steps of the surgical procedure are as follows:

1. Standard ophthalmic surgery techniques must be used to prepare the patient and the eye. The target area must be pretreated with mitomycin C (see Protocol Procedure Manual for dosing and intraoperative application details).
2. Surgeons may use their standard of care to obtain access to the surgical quadrant. The needle of the sterile XEN Injector preloaded with the XEN Gel Implant is advanced through the peripheral cornea and across the anterior chamber (ie, *ab interno*) toward the targeted quadrant. Corneal entry will be at least 1 to 2 mm anterior to the limbus (ie, not at the limbus or behind it) to ensure proper angulation on the Gel Implant up and away from the iris. The Gel Implant will be placed through the center of the angle.
3. Once the needle is aligned with the desired entry point in the anterior chamber angle, the surgeon advances the needle in the anterior chamber angle and sclera until the surgeon is able to visualize the needle bevel as it exits the sclera into the subconjunctival space.

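### The patient instruction in Protocol 6.1.2.1 stops all topical IOP-lowering drugs on surgery day without limiting this to the study eye, contrary to 4.4.1.1 and 4.4.1

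*Protocol*

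**What the plan says.** Four places in the Protocol bear on the point.

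- **6.1.2.1 Preoperative Medications**, what the patient is to be told: "Patients must be instructed to discontinue all topical and systemic IOP-lowering medications on the day of surgery".
- **4.4.1.1 IOP-lowering Medications**, the rule itself: "Systemic and topical (study eye only) IOP-lowering medications, will be suspended on the day of surgery".
- **4.4.1 Permissible Medications/Treatments**, the fellow eye: "Treatment of the fellow (non-study) eye is not restricted, and fellow eyes will receive appropriate medical and/or surgical treatment, including IOP-lowering medications", at the investigator's discretion.
- **4.4.2 Prohibited Medications/Treatments**, a restatement of the suspension: "Topical and systemic IOP-lowering medications must be suspended on the day of surgery". A bullet later in the same section does name the eye: "Use of any nonstudy topical ophthalmic medications in the study eye, including use of IOP-lowering medications".

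Section 6.2 tells patients to follow the medication instructions in 6.1.2.1 and 6.1.3.1. It does not send them to 4.4.1.1.

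**The concern.** The study-eye limit appears where the rule is set and is missing where the rule becomes an instruction to the patient. The word *all* makes that instruction broader than the rule.

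Implantation is unilateral (4.1), so every patient with two eyes has a fellow eye outside the study treatment. Some fellow eyes will be on drops: 5.2 provides for patients in whom both eyes qualify, and SAP 8.4.2 tabulates IOP-lowering drugs separately for study and fellow eyes. A patient who follows 6.1.2.1 to the letter would stop those drops. A site that rightly continues them would depart from the letter of 6.1.2.1, although 10.2 and 12.2 hold sites to the protocol.

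What is at stake is the safety of the fellow eye and consistent practice across sites. The effectiveness results are not involved.

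**Working it through.** The plan states no figure on this point, so the check is a comparison of the texts, followed by a simple count of days and visits.

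**Comparison of the suspension rules**

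| Section | Topical drugs | Systemic drugs |
|---|---|---|
| 4.4.1.1 | Suspended, study eye only | Suspended |
| 4.4.1 | Fellow-eye treatment left open, IOP-lowering drugs included | Not addressed by eye |
| 4.4.2, suspension sentence | Suspended, no eye named | Suspended |
| 6.1.2.1 | All discontinued, no eye named | Discontinued |

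The systemic column is consistent, so the conflict is confined to topical drugs. Nothing else in 6.1.2.1 supplies the limit: Table 6-1 names no eye, and there is no cross-reference to 4.4.1.1.

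**What would reveal a mistake**

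- Day 1, before implantation (6.1.3): the list includes "Concomitant medications (systemic and ophthalmic [both eyes]) and procedures".
- Every visit (4.4.1): "The use of any concomitant medication or procedure, prescription or over-the-counter, is to be recorded". Table 1-1 marks this row at Day 1 and at all later visits. However, 6.1.4 introduces the follow-up list, which includes concomitant medications, as information on the study eye.
- Scheduled tonometry (Table 1-1): the IOP row is marked for the study eye only at Day 2, Day 8, Week 2 and Months 1, 3, 6, 8 and 10. That is 8 visits, and fellow-eye IOP is scheduled at 0 of the 8.

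So a medication review could find the error, but scheduled IOP measurement from Day 2 to Month 10 would not.

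**Length of the gap, as an illustration**

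Days of fellow-eye drops missed = day of discovery − 1, counting from Day 1, the day of surgery.

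- Found at the Day 1 review: 1 − 1 = 0 days (at most a dose).
- Found at Day 2: 2 − 1 = 1 day.
- Found at Day 8 ± 2, that is Day 6 to Day 10: 6 − 1 = 5 days to 10 − 1 = 9 days.

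The last case requires both the Day 1 and the Day 2 reviews to miss it. The documents give no basis for a probability, so these are not estimates.

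**The case against.** The best answer is that no competent site would be misled. The correct rule is stated in 4.4.1.1 and supported by 4.4.1, and investigators, who read both, are the ones who instruct patients. Section 6.1.2.1 concerns preparation for surgery on one eye. Tables 6-1 and 6-2 also name no eye, yet the study eye is the natural reading. *All* may mean all drug classes, not both eyes. The 4.4.2 sentence looks like a shortened restatement, and the sentence after it points to 4.4.1.1. The Protocol Procedure Manual may also carry eye-specific wording. As for monitoring, 6.3 allows extra examinations whenever safety calls for them.

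Much of this stands. The intent is recoverable, and the 4.4.2 sentence is better described as an omission than as a competing rule. The absence of scheduled fellow-eye tonometry is a separate design choice; it matters here only because it removes one way of noticing the error.

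It does not dispose of the point. The drug-class reading is possible, but the sentence does not say so. The reference in 4.4.2 to 4.4.1.1 concerns restarting drugs after surgery, not which eye stops. Section 6.1.2.1 cites the Manual for the preoperative medications, not for the discontinuation sentence, and the Manual is not available to check. That the right rule appears elsewhere shows how to correct the instruction; it does not make the instruction correct.

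**Conclusion.** The inconsistency is real and minor. Two sentences, in 6.1.2.1 and 4.4.2, omit the study-eye limit that 4.4.1.1 sets and 4.4.1 supports. The one in 6.1.2.1 matters more, because it is the patient instruction and says *all*.

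The likely effect is nil to about a day of missed fellow-eye drops if the planned reviews work, and 5 to 9 days if the error survives to the Day 8 visit. This assumes a patient with a treated fellow eye who follows the literal text. The number of such patients is not given, so no count is claimed. The primary analysis, the other effectiveness analyses and the sample size are unaffected.

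**What to change.** - **6.1.2.1:** insert *(study eye only)* after *topical*, drop *all*, and add a clause saying that topical IOP-lowering drugs in the fellow eye continue as the investigator directs.
- **4.4.2, suspension sentence:** insert *(study eye only)* after *Topical*.

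The cost is a two-sentence wording amendment, with sponsor approval and ethics committee approval where 12.2 requires it, and a note to the approximately 15 sites. It can travel with another amendment, with the site note pointing to 4.4.1.1 in the meantime. No visits, data or analyses are added.
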